10. STUDY CALENDAR

10.1 Pre-Treatment Evaluations

All required tests must be performed within 21 days of the start of treatment.

Clinical Evaluations:

1. A complete history with full details of the patient's previous treatment and response will be obtained.
2. A complete physical examination.
3. Marrow aspiration and biopsy with cytogenetics, flow cytometry, and molecular genetic NGS sequencing panel (e.g. "heme snapshot" or "rapid heme" panel, per local site). Patients are eligible who have a dry aspirate.
4. Echocardiogram or MUGA to assess ejection fraction.
5. Chest X-ray
6. Performance Status
7. All study participants must be registered into the mandatory REMS program, and be willing and able to comply with the requirements of REMS.

Laboratory Evaluations:

1. CBC with differential
2. Comprehensive chemistry profile, including measures of hepatic and renal function, such as electrolytes, BUN, creatinine, alkaline phosphate, bilirubin, and transaminases, as per institutional guidelines.
3. Pregnancy Test (serum or urine) in child bearing female. Refer to inclusion criteria 3.1.13 for details.

10.2 Bone Marrow Assessments

All patients will have bone marrow examined at the time of count recovery or, if counts have not yet recovered, at Day +35 +/- 3 days. Patients with persistent leukemia will be followed for overall survival as noted in section 10.4.

Patients who have count recovery within one week of the Day 35 marrow do not need a repeat bone marrow. Patients who have not experienced count recovery by Day 45 will have a marrow evaluation performed at Day 45+/-3 days regardless of counts. Patients may have additional bone marrows performed as clinically indicated.

10.3 Post Treatment Evaluations

Standard post-treatment testing, including complete blood counts and, serum chemistries will be

CONFIDENTIAL

This document is confidential. Do not disclose or use except as authorized.

performed per institutional guidelines and consistent with clinical good practice. Suggested practice would be to perform three times weekly.

10.4 Long Term Follow Up

Participants will be followed for at least 50 days after the start of protocol treatment to assess for response to treatment and adverse events. At the completion of the study treatment, participants will be followed for relapse and overall survival outcomes for a total of 3 years from the start of treatment. These outcomes should be assessed at approximately 3 months after treatment, and then approximately every six months until the 3 year follow-up has been reached.

Patients removed from the study treatment early, for instance patients with refractory disease who go onto another therapy within 45 days of the study therapy, and will continue to be followed for relapse and survival for up to three years following initiation of study treatment.

Participants removed from protocol therapy for unacceptable adverse event(s) will be followed until resolution or stabilization of the adverse event. They will then also be followed at the above approximate intervals for relapse and survival outcomes.

Baseline evaluations are to be conducted within 21 days prior to the start of protocol therapy.

Assessments must be performed prior to administration of any study agent. Study assessments should be administered within \pm 3 days of the protocol-specified date, unless otherwise noted.

Table 6. Required Study Data.

	Pre-treatment (within 21 days)	Weekly (+/- 3 days)	Count recovery or Day +35 (+/- 3 days)	Day +38	Day +45 +/- 3 days
Medical History and Physical Exam	X				
CBC with diff	X	X (Diff optional)			X
Comprehensive chemistry with renal and liver functions ¹	X	X			X
ABO/Rh	X				X
Bone marrow biopsy and aspirate ²	X		X		X
Informed Consent	X				
History and physical	X	X			X
Performance Status	X				
EKG	X				
MUGA or ECHO	X				

CONFIDENTIAL

This document is confidential. Do not disclose or use except as authorized.

Chest x-ray	X				
Toxicity assessment ⁴	X	ongoing throughout			
Enroll in REMS	X				
Pregnancy Test Child Bearing Female	X			X	
Optional Research Studies	X ⁵	b	X		

¹ Chemistry testing to include creatinine, eGFR, BUN, potassium, sodium, chloride, HCO3, glucose, magnesium, phosphorus, calcium. Liver function testing to include ALT, AST, total bilirubin, alkaline phosphatase, albumin.

² All patients will have bone marrow examined at count recovery or at Day +35 +/- 3 days. Patient will be off treatment if persistent leukemia or need for further treatment. Patients who have count recovery within one week of the Day 35 marrow do not need a repeat bone marrow. Patients who have not experienced count recovery by Day 45 will have marrow at Day 45+/-3 days regardless of counts. Patients may have additional bone marrows performed as clinically indicated.

³The day 4 peripheral blood research sample should be obtained prior to the initiation of MEC chemotherapy (may be obtained before or after lenalidomide on that day).

⁴ Toxicity will be assessed from the time of first dose of study treatment through 30 days past the last dose of study treatment.

⁵Molecular testing (correlative 1) may be performed at the time of disease relapse and within 2 months of study enrollment, provided no intervening systemic chemotherapy has been administered (excluding hydroxyurea or 6MP).

^bSamples for optional correlative 4 may be collected at baseline prior to chemotherapy, and on day 3 of treatment (or day 2 or 4 if on a weekend, but prior to MEC administration).

11. MEASUREMENT OF EFFECT

11.1 Count Recovery

11.1.1 Time to Neutrophil Recovery

The time to neutrophil engraftment is defined as the first 3 consecutive days of absolute neutrophil count >500.

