1.3 Secondary Objectives

1. To evaluate the days to neutrophil recovery (the first of 3 days of ANC >500)
2. To evaluate the days to platelet recovery (platelet count >20K unsupported)
3. To evaluate the treatment-related mortality (the number of non-relapse related deaths in the first 50 days of starting treatment)
4. To evaluate the transfusion support (the number of red blood cell and platelet transfusions needed in the first 50 days of treatment)
5. To determine if certain genetic profiles of the leukemia predict for better response (optional correlate)

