11.1.2 Time to Platelet Recovery

Platelet recovery is defined as a platelet count $\geq 20,000/\mu\text{L}$ for three consecutive measurements over three or more days. The first of the three days will be designated the day of platelet engraftment. Subjects must not have had platelet transfusions during the preceding 3 days or in the following 7 days after the day of engraftment, unless the platelet transfusion is being given specifically to achieve a platelet threshold to allow an elective invasive procedure, such as a central catheter removal. The time to a platelet count $\geq 100,000/\mu\text{L}$ will be collected as well.

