13.1.1 Evaluation of toxicity

All participants will be evaluable for toxicity from the time of their first treatment up until day 50 or the initiation of other therapy. In the phase I study of 35 patients, 3 dose limiting toxicities were noted due to prolonged count recovery. In the current study, we will monitor for toxicities and assess them as a part of the two stage design described above. If, within the first 10 patients on study, 3 or more experience prolonged neutrophil or platelet recovery beyond day 45 in the absence of disease, or other unacceptable toxicities felt related to the study regimen, we will put the study on hold to investigate further enrollment. The probability of putting the study on hold is 7%, if the true probability of delayed count recovery is 10%.

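### Neutrophil recovery is defined on three consecutive days of ANC, but the required weekly counts, with an optional differential, cannot show or date it

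*Combined protocol and SAP*

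**What the plan says.** **Definition.** Section 11.1.1 sets neutrophil recovery at "the first 3 consecutive days of absolute neutrophil count >500". The synopsis and Section 1.3, where this is secondary objective 1, give "the first of 3 days of ANC >500", without the word consecutive. Section 13 commits to reporting the proportion recovered and the median days to recovery by the Section 11.1 definitions.

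**Schedule.** The table in Section 10.4 is headed "Table 6. Required Study Data". Its CBC row has a weekly column (+/- 3 days) whose cell begins "X (Diff optional". The same row has an unqualified entry at Day +45 +/- 3 days. Section 10.3 says that post-treatment counts are "performed per institutional guidelines and consistent with clinical good practice" and adds: "Suggested practice would be to perform three times weekly".

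**Platelets, for comparison.** Section 11.1.2 requires the platelet threshold to be met "for three consecutive measurements over three or more days".

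**Hold rule.** Section 13.1.1 puts the study on hold if 3 or more of the first 10 patients have "prolonged neutrophil or platelet recovery beyond day 45 in the absence of disease", or other unacceptable toxicity felt to be related to the regimen. Section 10.2 requires a marrow at Day 45 +/- 3 if counts have not recovered.

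**The concern.** An endpoint defined on consecutive days needs daily ANC values around recovery. The binding schedule asks for one count a week and lets the site omit the differential from which the ANC comes. A patient followed exactly as required may have no value that bears on the definition. The analyst would then have to report the patient as not recovered, or substitute another rule after the fact, such as the first weekly value above 500. Sites that count daily in hospital and sites that discharge early would produce different recovery dates for reasons unrelated to the treatment. The two wordings of the definition leave further room for sites to differ.

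Count recovery is also the main safety signal carried over from Phase I, and it feeds the hold rule. It therefore has to be asked whether the same gap weakens that rule.

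**Working it through.** **1. The plan's own figure.** The hold rule is 3 or more of 10 at a true rate of 10%:

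P(X >= 3) = 1 - (0.9^10 + 10 x 0.1 x 0.9^9 + 45 x 0.1^2 x 0.9^8) = 1 - (0.3487 + 0.3874 + 0.1937) = 0.070.

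This reproduces the stated 7%.

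**2. Can the schedule contain three consecutive days?**
- Weekly: three successive visits nominally span 14 days. With the +/- 3 day windows fully used they span at least 14 - 6 = 8 days, so they cannot be consecutive days.
- Monday/Wednesday/Friday: this pattern has no three consecutive calendar days either.
- Daily: yes, but daily counts are not required.
- One narrow exception: the windows of the Day 42, 45 and 49 visits (Days 39-45, 42-48 and 46-52) could by chance give adjacent days, if the weekly differentials were done.

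**3. How late is recovery dated if the first qualifying ANC is used?** Assume that the ANC stays above 500 once recovered, that every weekly differential is done (which favours the plan), and that recovery falls at random between visits. The mean delay is then E[G^2] / (2 E[G]), where G is the gap between visits.
- Weekly, each visit uniform within +/- 3 days: each offset has variance 6^2/12 = 3, so the gap has variance 6. E[G^2] = 49 + 6 = 55, and the delay is 55/14 = 3.9 days. Simulation gives the same mean and a 95th percentile of 8.8 days.
- Weekly on fixed days: 49/14 = 3.5 days.
- Monday/Wednesday/Friday (gaps 2, 2, 3): (4 + 4 + 9)/14 = 1.2 days.

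The spread of recovery times does not enter the formula. In simulation the weekly mean stays at 3.9 days for log-SD 0.15 to 0.35.

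**4. Effect on the neutrophil part of the hold rule.** Assume lognormal recovery times with the Phase I median of 30 days (Section 2.4.1). The log-SD is not in the documents, so 0.25 is an assumption. The true share beyond Day 45 is 1 - Phi(ln(45/30)/0.25) = 1 - Phi(1.62) = 5.2%. With the required Day 45 +/- 3 differential included (400,000 draws):

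| Reading of the Day 45 visit | Recorded beyond Day 45 | P(3 or more of 10) |
|---|---|---|
| True recovery time | 5.2% | 1.3% |
| By ANC status at that visit | 5.5% | 1.5% |
| By date of first value above 500, so a visit on Days 46-48 counts as late | 7.9% | 3.9% |

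The true share itself runs from 0.3% (log-SD 0.15) to 12% (log-SD 0.35). Uncertainty about the spread is therefore larger than the effect of the schedule.

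**The case against.** **Table 6 is a minimum.** Counts are taken by institutional practice. Section 10.2 requires a marrow at count recovery, so sites must notice recovery when it happens, and complete remission itself needs an ANC above 1000 (Section 11.5). Many patients will have daily inpatient counts. This stands as a statement about likely practice: it would be wrong to say that no patient will ever have the data. It does not answer the point about required data, and even the suggested frequency does not meet the literal definition.

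**The endpoint is secondary and descriptive.** This is correct. No test or decision uses the median days to recovery, and that limits the severity.

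**The hold rule is largely covered.** A reader might infer that the required data cannot support the Day 45 hold rule at all. The documents do not bear that out. Table 6 requires a CBC with differential at Day 45 +/- 3. Section 10.2 requires a marrow then if counts have not recovered, which addresses the absence of disease. The platelet and other-toxicity triggers need no differential, and weekly counts can satisfy the platelet definition. The consequence of the rule is a hold to investigate, not automatic closure. What survives is narrower: one ANC in a Day 42-48 window cannot confirm three days above 500, nor place recovery exactly before or after Day 45.

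**Conclusion.** The definition in Section 11.1.1 and the required schedule in Table 6 do not fit together. On the required weekly data, secondary objective 1 cannot be documented as defined, and an ANC need not be recorded at all. Using the first qualifying weekly value would date recovery about 3.9 days late on average, against about 1.2 days with three tests a week. That result rests on the visit windows and on recovery falling at random between visits; it hardly depends on the assumed spread of recovery times.

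The effect on the hold rule is limited. Under the assumed lognormal (median 30 days, log-SD 0.25) the recorded share beyond Day 45 is 5.5% to 7.9% against a true 5.2%, depending on how the Day 45 visit is read. These percentages are illustrative, because the documents do not give the spread.

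The point is minor, but real and cheap to correct.

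**What to change.** - **Section 11.1.1:** define ANC recovery as the first of three consecutive measurements above 500 spanning at least three days, in parallel with Section 11.1.2.
- **Synopsis and Section 1.3:** use the same wording, so that only one definition is in force.
- **Table 6:** remove the optional marking, so that an ANC is recorded at each post-treatment CBC until recovery or Day 50. Preferably require the three-times-weekly frequency that Section 10.3 already suggests. At that frequency three measurements span 4 or 5 days, so a recovery first seen on Day 45 can be confirmed by Day 50; three weekly measurements nominally span 14 days.

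The cost is amendment wording and a few extra outpatient differentials.

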11.1.2 Time to Platelet Recovery

Platelet recovery is defined as a platelet count $\geq 20,000/\mu\text{L}$ for three consecutive measurements over three or more days. The first of the three days will be designated the day of platelet engraftment. Subjects must not have had platelet transfusions during the preceding 3 days or in the following 7 days after the day of engraftment, unless the platelet transfusion is being given specifically to achieve a platelet threshold to allow an elective invasive procedure, such as a central catheter removal. The time to a platelet count $\geq 100,000/\mu\text{L}$ will be collected as well.

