6.1 Toxicity Management

Significant toxicity is expected in this leukemia reinduction protocol. Patients will receive supportive care and medical management of toxicity.

Antiemetics are recommended for management of nausea and vomiting.

Stool cultures for C. Diff are recommended for patients with diarrhea. If negative, antidiarrheals should be used as clinically indicated

For management of neutropenia/fever myeloid growth factors can be considered. Platelet transfusions should be considered for management of patients with a platelet count of <10K or bleeding.

Local steroid creams are recommended as clinically indicated for the management of rashes.

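### The elective-procedure exception in the platelet-recovery definition also covers the 3 days before engraftment, so a count raised by a procedural transfusion can be scored as unsupported recovery

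*Combined protocol and SAP*

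**What the plan says.** The synopsis and Section 1.3 give the secondary objective: "To evaluate the days to platelet recovery (platelet count >20K unsupported".

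Section 11.1.2 turns it into a scoring rule. The count must be at least 20,000/µL "for three consecutive measurements over three or more days", and the date scored is the start of that run: "The first of the three days will be designated the day of platelet engraftment". The transfusion condition follows: "Subjects must not have had platelet transfusions during the preceding 3 days or in the following 7 days after the day of engraftment, unless the". What comes after those words is a single exception, for platelets given so that a planned procedure can go ahead; taking out a central line is the example offered.

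Section 13 reports, descriptively, the proportion of patients who recover by the Section 11.1 definition and the median days to recovery. Section 13.1.1 uses delayed recovery as one trigger for a hold, if among the first 10 patients "3 or more experience prolonged neutrophil or platelet recovery beyond day 45 in the absence of disease", or other unacceptable toxicity occurs. Section 13.1.1 does not cite Section 11.1.

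**The concern.** The two windows do different jobs. The 7 days afterwards show that recovery was sustained. Forgiving a procedural transfusion there is sensible, since a patient who has already recovered should not lose that status over a line removal. The 3 days beforehand keep a recently transfused count from starting the run. Forgiving a transfusion there removes the safeguard that makes the count unsupported.

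Both windows stand in one clause and a single exception follows them. Nothing confines it to the later window. No other section says that counts after an excepted transfusion are disregarded or that the look-back restarts. The second and third counts of the run also fall in the later window, so an excepted transfusion between counts can prop up the run as well.

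Measured against an unsupported count, the exception in the earlier window can err in one direction only: recovery dated too early, or recorded when it did not happen.

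**Working it through.** **1. The plan's own figure.** Section 13.1.1 states a 7% chance of a hold at a true delayed-recovery rate of 10%. With X ~ Binomial(10, 0.10), P(X ≥ 3) = 0.0702. It reproduces.

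**2. One record.** Assumed, not in the documents: native count flat at 15K, increment 30K, half-life 1.5 days. Count d days after transfusion = 15 + 30 × 2^(−d/1.5).

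- Procedural transfusion on Day 29, inside the 3 days before Day 30.
- Day 30 (d = 1): 33.9K. Day 31: 26.9K. Day 32: 22.5K.
- All three are at least 20K over three days and the transfusion is excepted. If no other platelets are given in the next 7 days, recovery is scored on Day 30, although the native count never reached 20K.

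The 7-day condition need not catch this. Section 6.1 says "Platelet transfusions should be considered for management of patients with a platelet count of <10K or bleeding", so a stable patient between 10K and 20K may receive none.

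**3. Range of assumptions.** Native count uniform on 10-20K and flat; increment normal with mean m = 20, 30 or 40K and SD 10K; half-life h = 1, 1.5, 2 or 3 days. Counts fall after transfusion, so the run qualifies exactly when the third count, on day d₃, is at least 20K. For a given increment I (in K) this has probability min(1, I × 2^(−d₃/h) / 10). The central case is m = 30K, h = 1.5 days. The formula column puts I = 30; the simulated columns let I vary.

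| Counts on days after transfusion | Formula at I = 30 | Simulated, central | Simulated, range |
|---|---|---|---|
| 1, 2, 3 (daily) | 30 × 2^(−2) / 10 = 0.75 | 73% | 25-100% |
| 1, 3, 5 (every second day) | 30 × 2^(−3.33) / 10 = 0.30 | 30% | 6-96% |

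Section 10.3 suggests counts three times weekly, close to the second row. Table 6 asks only for a weekly CBC. With counts on days 1, 8 and 15, the formula gives 30 × 2^(−10) / 10 = 0.003 in the central case and 40 × 2^(−5) / 10 = 0.125 in the most extreme one (m = 40K, h = 3 days).

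**4. Hold rule, if it uses the Section 11.1.2 definition.** Suppose a share k of truly delayed patients is masked. Then P(hold) = P(Binomial(10, p(1 − k)) ≥ 3).

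| True rate p | k = 0 | k = 10% | k = 20% |
|---|---|---|---|
| 10% (planned) | 7.0% | 5.4% | 4.0% |
| 30% | 62% | 53% | 44% |

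The values of k and the 30% rate are illustrations without a source in the documents.

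**5. Same model with qualifying counts starting 3 days after transfusion.** Daily counts on days 3, 4 and 5: 30 × 2^(−3.33) / 10 = 0.30 (range 6-96%). Every second day, on days 3, 5 and 7: 30 × 2^(−4.67) / 10 = 0.12. The record in step 2 is now rejected, because its day-4 count is 19.7K.

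**The case against.** The strongest reply is that this is a wording ambiguity whose effect nobody can size. The exception covers only elective-procedure transfusions, three consecutive counts are still required, and the endpoint is a descriptive proportion and median. Every percentage above is conditional on a patient at 10-20K receiving such a transfusion just before the run. Section 5.4.1 suggests central access before chemotherapy, which says nothing about procedures near recovery. Section 6.1 only asks that transfusion be considered below 10K or for bleeding, and Sections 5.4.1 and 11.6 defer to local practice, so some of these patients would be transfused again and fail the 7-day condition. All of this stands. It limits the size of the point, not the reading of the text.

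Three stronger readings are tempting and unsupported:

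- A reader might place the transfusion on the engraftment day itself, which gives 92% (daily) and 47% (every second day). Taken literally, that day lies in neither window, so the exception is not what lets those counts through.
- A reader might infer that the safety hold is compromised. Section 13.1.1 does not cite Section 11.1, and a patient masked on platelets can still count through neutrophils or other toxicity. Nor is the phase I figure of 2 of 6 without count recovery at Day 42 a suitable planning rate. It comes from the 14-day lenalidomide schedule; on the 10-day, 50 mg schedule used here, Section 2.4.1 reports prolonged count recovery in 1 of 13.
- A reader might suspect the primary endpoint. Section 11.5 defines CR and CRp by a separate 100,000/mm³ platelet threshold, so the two-stage design is untouched.

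**Conclusion.** The point holds as a minor one. As written, Section 11.1.2 can score a transfusion-raised count as platelet recovery, contrary to the unsupported count in the synopsis and Section 1.3. Attaching the exception to the later window alone is a possible intention, but the sentence does not say so.

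For a patient who has such a transfusion, the chance of false recovery is substantial with frequent counts and small with weekly ones, under kinetics that are assumed throughout. The effect on the reported proportion and median cannot be stated without the frequency of these transfusions, which the documents do not give. An effect on the hold rule depends on Section 13.1.1 adopting the same definition. At the planned 10% rate it would be 1.6 to 3.0 percentage points (7.0% to 5.4-4.0%).

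**What to change.** In Section 11.1.2:

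- limit the elective-procedure exception to the 7 days after engraftment;
- require the first qualifying count to be at least 3 days after any platelet transfusion, whatever its indication;
- do not use counts within 3 days after any platelet transfusion as qualifying counts. This also closes the gaps on the engraftment day and inside the run.

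State whether the 3 days are elapsed time or whole calendar days, so that the new wording is no looser than the present look-back. Cite this definition in Section 13.1.1 for the Day 45 criterion.

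The change concerns scoring only, not when anyone is transfused. It reduces transfusion-supported counts without eliminating them: in the central case from 73% to 30% with daily counts and from 30% to 12% every second day. The report should not describe it as a complete cure.

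The cost is a sentence or two of text, and some patients' recovery dated a few days later. Transfusion dates are needed, and Section 11.6 asks only for numbers of transfusions; but the existing 3- and 7-day windows cannot be applied without dates, so this adds no new data requirement.
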